10.4.1 Reference Measurements (to be collected from patient charts)

The following parameters will be measured and recorded at the time of Randomization as well as on subsequent dates using values closest in time to 8:00 A.M. on the days specified in the Time-Events Schedule (**Appendix A**). The following conditions will be ensured prior to measurements: no endobronchial suctioning for 10 minutes; no invasive procedures or ventilator changes for 30 minutes. All vascular pressures will be zero-referenced to the mid-axillary line..

1. If receiving assisted ventilation, record daily up to day 7:
 - a. Tidal volume, FiO₂, PEEP, inspiratory plateau pressure, and mean airway pressures
 - b. Pressure during inspiration if on a pressure targeted mode (PSV, PCV, etc)
 - c. Arterial PaO₂, PaCO₂, pH and transcutaneous oxygen saturation
2. Fluid intake and output
3. Vital signs: Heart rate, systolic and diastolic blood pressure, body temperature, CVP
4. Modified Brussels Score data on days 0 through 14
 - a. Vasopressor use (Y/N), lowest systolic blood pressure, creatinine, bilirubin, and platelet count for the day
5. The date and value of the highest creatinine between days 15 and 28
6. Safety laboratory studies: all creatinine and bilirubin measurements will be recorded as above. Creatinine, bilirubin and ALT will be measured and recorded as safety labs on day 7 if not obtained as part of clinical care.
7. Data regarding infections, including:
 - a. Surgical site and wound infections by CDC criteria
 - b. Ventilator associated or nosocomial pneumonia as diagnosed by CDC criteria
 - c. Culture-proven bacteremia
 - d. SARS-CoV-2 virus infection
8. Blood product transfusions
9. On-study procedures and surgical interventions
10. Co-enrollment in randomized clinical trials of other interventions and treatments related to SARS-CoV-2 infection
11. Inpatient medications (selected)
12. Must include all data needed for the 4-point acute lung injury score (including frontal chest radiograph), SOFA score, OSCI score and trauma registry index (if applicable)
13. D-dimer, lymphocyte count, neutrophil count, fibrinogen, ferritin and serum C-reactive protein (if applicable)

10.4.2 Specimen Collection

1. Date and time of specimen collection
2. Time of specimen processing and storage

10.5 *Endpoint Determinations*

1. Vital status at 60 days
2. Brussels Organ dysfunction failures at days 0-14
3. SOFA score at 3 and 7 days
4. Oxygenation index ($\text{PaO}_2/\text{FiO}_2$ and mean airway pressure) at 6, 12, 18, 24, 30 and 36 hours after the initiation of study product infusion as well as on days 2, 3, and 7 if still being ventilated with positive pressure (cannot be calculated if patient is on pressure support, as the mean airway pressure is not reliable)
5. Ventilatory ratio at 6, 12, 18, 24, 30, 36 hours after the initiation of study product infusion, and on days 2, 3, 7
6. Incidence of barotrauma on days 1, 2, 3 and 7
7. Time when patient achieves pressure support ventilation with 5 cmH_2O and 5 cmH_2O positive end-expiratory pressure for 2 hours
8. Time of initiation of unassisted breathing (assuming a patient achieves 48 consecutive hours of unassisted breathing)
9. Need for re-instituting assisted or mechanical ventilation after achieving 48 consecutive hours of unassisted breathing
10. Status 48 hours after initiation of unassisted breathing
11. Need for, timing, and duration of dialysis; change in renal function as measured by creatinine
12. ICU length of stay in calendar days including ICU days after readmission to ICU
13. Hospital length of stay in calendar days
14. Discharge diagnoses and discharge disposition (home, other facility, with or without assisted ventilation)
15. WHO Ordinal Scale of Clinical Assessment at days 7, 14 and 28

10.6 *Assessments After Hospitalization*

A health status questionnaire will be conducted at 28 days, 60 days and 6 months through telephone interviews.

11 Statistical Plan

The Statistical Analysis Plan has been written along with this Protocol and provides the details of the statistical methodologies applied to this Phase 2b trial.

11.1 Sample Size Determination

The sample size for this trial will be 60 patients in the hMSCs arm and 60 patients in the placebo arm, for a total of 120 patients with a balanced randomization of patients with $\text{PaO}_2:\text{FiO}_2 < 150$ mmHg and patients with trauma. This sample size was determined on the basis of feasibility.

Given the sample size of 60 per treatment condition, in this multisite, randomized trial using oxygenation index as the primary outcome and measures taken at 6 time points, it is estimated the study will have 80% power to detect a difference between conditions for an effect size as low as 0.43. Using the pilot data from Day 4, for example, this would translate to approximately a difference of 1.29 in the oxygenation index.

11.2 Statistical Methods for Primary and Secondary Endpoints

Descriptive summary statistics (e.g. means and standard deviations, or median with inter-quartile, as appropriate) will be used to summarize the primary and secondary endpoints by study treatment. The primary and secondary efficacy endpoints will also be analyzed using appropriate models.

The primary endpoint, change in the oxygenation index over time, will be compared between treatment conditions using a linear mixed-effects regression model. The model will be estimated using likelihood estimation which will allow the inclusion of all collected data, regardless of the number of assessments available for assessment. Terms in the model will include the two stratification variables, treatment condition (active or placebo), time of assessment, condition-by-time, recruitment site and a site-by-treatment interaction term. A test of the treatment condition will directly test the main research question. Covariates identified by preliminary analysis as potentially confounding due to baseline differences will be added to the model.

The data analysis plan for secondary efficacy and safety endpoints has been provided in the Statistical Analysis Plan.

The primary and secondary endpoints (including clinical and biological data) will be adjusted for COVID-19 infection as a cause of ARDS, which is adjudicated by the study physicians.

11.3 Subject Population(s) for Analysis

A total of three populations will be used for all summaries and analyses. Subjects who have satisfied the population criteria will be classified in the designated population and will only be included in analyses for which they have available data.

Intent-to-Treat (ITT) Population

The primary analysis for this trial will be an intention-to-treat (ITT) analysis based on randomization to either hMSCs or placebo.

Since the study treatment is a single infusion of study product, a subject is unlikely to be withdrawn by investigators due to safety concerns because there is only a single treatment to be administered. However, a surrogate or subject may withdraw consent for study participation either before, during

or after study product administration. For subjects who are withdrawn prior to the initiation of study product infusion, they will not be included in ITT population. For subjects who are withdrawn during or after study product administration, they will be included in ITT population.

The ITT population will be used to present primary efficacy endpoint and secondary efficacy endpoints by allocated randomization. Subjects will be summarized according to the treatment to which they were randomized, regardless of which treatment they actually received.

Per Protocol Population

It is possible that there will be a number of deviations from the trial protocol (e.g. non-compliance with the allocated intervention, non-adherence to other elements of the protocol, et al.) The Per Protocol (PP) population is defined as all patients who will complete the study without major protocol deviations. The PP population will be fixed following clinical review of all protocol deviations at the end of the study and prior to unblinding and data locking. Due to the blinding feature of the study, the analyses of endpoints using PP population will not be feasible in the interim report to DSMB. However, as a sensitivity analysis, the analysis of efficacy and safety endpoints using PP population will be included in the final study report.

Safety Population

The Safety population will be used for the analysis of safety, including adverse events, toxicity and safety laboratory evaluation. In this study, the Safety population is defined as all randomized who started the study product administration, regardless of infusion completion.

Due to the blinding feature of the trial, the safety and adverse events will be summarized using ITT population in the interim report for 60 patients to the DSMB. However, in the final report, the safety summaries and adverse events listings will be grouped by actual treatment received.

12 Safety and Adverse Events

12.1 Definitions

Investigators will determine daily if any clinical adverse experiences occur during the period from enrollment through study day 28 after investigational product administration. The investigator will evaluate any changes in laboratory values or physical signs, and will determine if the change is clinically important and different from what is expected in the course of treatment of patients with ARDS.

For this trial, a reportable adverse event is defined as:

Any clinically important untoward medical occurrence in a patient receiving study product which is different from what is expected in the clinical course of a patient with ARDS, or:

1. Any clinically important, untoward medical occurrence that is thought to be associated with the study product, regardless of the “expectedness” of the event for a patient with ALI, or
2. The following pre-specified infusion associated events occurring within 6 hours from the start of study product will always be reported as adverse events:

- If on a vasopressor, an increase in vasopressor dose greater than or equal to the following:
 - Norepinephrine: 10 mcg/min
 - Phenylephrine: 100 mcg/min
 - Dopamine: 10 mcg/kg/min
 - Epinephrine: 0.1 mcg/kg/min
 - Addition of a third vasopressor
- New cardiac arrhythmia requiring cardioversion OR ventricular tachycardia, ventricular fibrillation or asystole
- Hypoxemia requiring an increase in FiO₂ of 0.2 or more and an increase in PEEP of 5 cmH₂O or more to maintain SpO₂ in the target range of 88-95% that is not related to respiratory care/suctioning or ventilator dyssynchrony and persists for more than 30 minutes
- Clinical scenario consistent with transfusion incompatibility or transfusion-related infection (e.g. urticaria, new bronchospasm)

3. Any cardiac arrest or death that occurs within 24 hours from the start of study product will be reported as a pre-specified, infusion-associated significant event. Any cardiac arrest or death that occurs during the study period will be a reportable event that will be reviewed in detail.

A **serious adverse event** is any event that is fatal or immediately life threatening, is permanently disabling, or severely incapacitating, or requires or prolongs inpatient hospitalization. Important medical events that may not result in death, be life threatening, or require hospitalization may be considered serious adverse events when, based upon appropriate medical judgment, they may jeopardize the patient or subject and may require medical or surgical intervention to prevent one of the outcomes listed above.

1. 'Life-threatening' means that the patient was, in the view of the investigator, at immediate risk of death from the reaction as it occurred. This definition does not include a reaction that, had it occurred in a more serious form, might have caused death. Assessment of the cause of the event has no bearing on the assessment of the event's severity.
2. Adverse events will be considered to be study-related if the event follows a reasonable temporal sequence from a study procedure and could readily have been produced by the study procedure.

All adverse events that do not meet any of the criteria for serious should be regarded as **non-serious adverse events**.

An **unanticipated problem (UP)** is any incident, experience, or outcome that meets all of the following criteria (129):

- Unexpected, in terms of nature, severity, or frequency, given the research procedures that are described in the protocol-related documents, such as the IRB-approved research protocol and informed consent document, as well as the characteristics of the subject population being studied;
- Related or possibly related to participation in the research. In this guidance document, possibly related means there is a reasonable possibility that the incident, experience, or outcome may have been caused by the procedures involved in the research;

- Suggests that the research places subjects or others at a greater risk of harm (including physical, psychological, economic, or social harm) than was previously known or recognized.

Adverse Event Reporting Period

Reportable adverse events that occur during the 28 days following study product administration must be reported to the Investigator-Sponsor. Patients who are discharged home or outside facilities prior to study day 28 will be contacted after day 28 to determine vital status and for the occurrence of adverse events.

Prolonged Hospitalization or Surgery

All study subjects will be hospitalized at the time of study enrollment, by virtue of the disease being studied. Any adverse event that results in prolonged hospitalization should be documented and reported as a serious adverse event unless specifically instructed otherwise in this protocol.

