6.2.2 Safety Secondary Endpoints

Because the infusion of hMSCs could theoretically, as described above, cause transient occlusion of the pulmonary microcirculation which could be associated with a fall in systemic blood pressure, rising vasopressor dose, a rise in heart rate, an increase in arterial carbon dioxide concentration, or a fall in oxygenation, patients will be monitored closely during the study infusion for changes in these parameters. These events will be considered pre-specified infusion associated events if they occur within 6 hours of the initiation of study product infusion.

Pre-specified infusion associated events will be defined as:

(a) Within 6 hours of the initiation of study product infusion:

1. An increase in vasopressor dose greater than or equal to the following:
 - Norepinephrine: 10 mcg/min
 - Phenylephrine: 100 mcg/min
 - Dopamine: 10 mcg/kg/min
 - Epinephrine: 0.1 mcg/kg/min
 - Addition of a third vasopressor
2. New ventricular tachycardia, ventricular fibrillation or asystole
3. New cardiac arrhythmia requiring cardioversion
4. Hypoxemia requiring an increase in FiO₂ of 0.2 or more and an increase in PEEP of 5 cmH₂O or more to maintain SpO₂ in the target range of 88-95% that is not related to respiratory care/suctioning or ventilator dyssynchrony and persists for more than 30 minutes
5. Clinical scenario consistent with transfusion incompatibility or transfusion-related infection (e.g. urticaria, rash, new bronchospasm)

(b) Within 24 hours of the study product infusion:

1. Any cardiac arrest or death

We will also systematically collect and review the incidence and nature of serious adverse events that are different from what is expected in the clinical course of a critically ill patient with ARDS for the duration of the clinical trial (through day 28 from study product administration).

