9.4 Investigational Product Administration

The investigational product will be administered intravenously according to the following dose schedule. The investigational product (h MSCs or placebo) will be administered intravenously over approximately 60-80 minutes.

We will enroll 120 patients in a 1:1 blinded, randomized, placebo-controlled design with the dose of 10×10^6 viable cells/kg (60 patients treated with hMSCs and 60 controls), with viability determined at the time of cell preparation at UMMC. Safety analyses will be conducted by the independent DSMB, and the sponsor and investigators will remain blinded. The safety reviews will be conducted after treatment of 60 patients, and the trial will continue during these analyses.

Critically ill patients often experience minute-to-minute changes in vital signs. Investigators will begin the infusion of hMSCs after a stable baseline for 2 hours has been observed.

A. Stable baseline will be defined as:

- a. Transcutaneous oxygen saturation in the target range of 88-95% without any increase in ventilator settings **AND**
- b. Stable vasopressor use if the patient requires vasopressors for blood pressure support. The dose of vasopressor may be increased a small amount during this 2-hour period, predefined as: no more than a 5 mcg/min increase in norepinephrine dose; no more than a 50 mcg/min increase in phenylephrine dose; no more than a 5 mcg/kg/min increase in dopamine dose; and no more than a 0.05 mcg/kg/min increase in epinephrine dose.

B. The following patients will be considered clinically unstable and will **NOT** receive the study product:

- a. Patients requiring an increase in FiO₂ of 0.2 or more and an increase in PEEP of 5 or more to maintain SpO₂ in the target range of 88-95%
OR
- b. Patients who require 3 vasopressors for blood pressure support and/or the use of > 0.1 mcg/kg/min of epinephrine for blood pressure support,

OR

[figure not shown]
- c. Patients who do not meet stability criteria in the supine or prone position,
OR
- d. Patients who have evidence of ongoing bleeding by the requirement of more than 3 units of packed red blood cells during the prior 24 hours prior to randomization.

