12.2 Recording of Adverse Events

Assuring patient safety is an essential component of this protocol. Each participating investigator has primary responsibility for the safety of the individual participants under his or her care. The Principal Investigator at each study site will evaluate all clinically important adverse events. The Study Coordinator must view patient records for possible clinically important adverse events throughout the study period.

Expected events for ARDS are untoward clinical occurrences that are perceived by the investigator to occur with reasonable frequency in the day to day care of patients with ARDS treated in an ICU with mechanical ventilation. Examples of adverse events that are expected in the course of ARDS include transient hypoxemia, agitation, delirium, nosocomial infections, skin breakdown, and gastrointestinal bleeding. Such events, which are often the focus of prevention efforts as part of usual ICU care, will not be considered reportable adverse events unless the event is considered by the investigator to be associated with the study cell product or procedures, or is unexpectedly severe or frequent for an individual patient with ARDS. Examples of unexpectedly frequent adverse events would be repeated episodes of unexplained hypoxemia. This would be in contrast to an isolated episode of transient hypoxemia (e.g., Sp₀₂ ~85%), related to positioning or suctioning. This latter event would not be considered unexpected by nature, severity or frequency.

Organ failures related to ARDS or the patient's underlying condition that are systematically captured by the protocol should not be reported as adverse events *unless they are considered to be study related*.

All adverse events occurring during the study period must be reported in the patient's case report form. The clinical course of each event should be followed until resolution, stabilization, or until it has been determined that the study treatment or participation is not the cause. Serious adverse events that are still ongoing at the end of the study period must be followed to determine the final outcome. Any serious adverse event that occurs after the study period and is considered to be

possibly related to the study treatment or study participation should be recorded and reported immediately to the study sponsor (see **Section 12.3**).

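### Protocol 12.1 makes a 6-hour vasopressor increase automatically reportable only in patients on a vasopressor, while Protocol 6.2.2 and SAP 7.2.2 define the same event without that condition

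*Protocol*

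**What the plan says.** **Reporting rule.** Protocol 12.1 names pre-specified infusion-associated events "occurring within 6 hours from the start of study product will always be reported as adverse events". The vasopressor item opens "If on a vasopressor, an increase in vasopressor dose greater than or equal to the following". It then gives thresholds for norepinephrine, phenylephrine, dopamine and epinephrine, and adds a third vasopressor as a further trigger.

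**Endpoint definition.** Protocol 6.2.2 opens the same item "An increase in vasopressor dose greater than or equal to the following", and SAP 7.2.2 uses the same words. Neither conditions the item on prior vasopressor use.

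**Who may be infused.** Protocol 9.4 makes vasopressor use optional at the stable baseline: "Stable vasopressor use if the patient requires vasopressors for blood pressure support".

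**Other reporting routes.** Section 12.1 also makes an event reportable if it is "different from what is expected in the clinical course of a patient with ARDS", or under the limb "Any clinically important, untoward medical occurrence that is thought to be associated with the study product". Section 12.2 says of organ failures due to ARDS or the underlying condition that those "that are systematically captured by the protocol should not be reported as adverse events", unless they are thought to be study related.

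**Where the event is used.** It forms part of the secondary safety endpoint (Protocol 6.2.2, SAP 7.2.2) and of the safety analysis in SAP 12.7.11. Section 9.4 stops the infusion when such an event occurs. Sections 5 and 12.5 call for a DSMB safety evaluation once three subjects have pre-specified clinically important events or unexpected serious adverse events other than death. Section 12.3.3 sends such events to the DSMB as they arise.

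**The concern.** Two definitions of one event are in force. Sites work from 12.1 when deciding what to file; the analyst works from 6.2.2 and SAP 7.2.2 when deciding what to count. They part company for patients not on a vasopressor before the infusion, in whom a new vasopressor requirement may be the first sign of haemodynamic harm. A fall in blood pressure and a rising vasopressor dose are among the theoretical effects of the cells that Protocol 3.7.2.2 and 6.2.2 name.

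An automatic list spares a blinded investigator from deciding whether an early event in a very sick patient belongs to ARDS or to the infusion. The added condition hands that decision back for this group. If the decision goes against reporting, the event may be missing from the adverse-event listing and from what the DSMB sees.

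**Working it through.** No sample size, power or error rate is involved and the plan states no figure to reproduce. The check is a comparison of the texts.

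**1. The three definitions side by side.**

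| Element | Protocol 12.1 | Protocol 6.2.2 | SAP 7.2.2 |
|---|---|---|---|
| Role | always-report list | safety endpoint | safety endpoint |
| Must be on a vasopressor | yes | not stated | not stated |
| Norepinephrine, mcg/min | 10 | 10 | 10 |
| Phenylephrine, mcg/min | 100 | 100 | 100 |
| Dopamine, mcg/kg/min | 10 | 10 | 10 |
| Epinephrine, mcg/kg/min | 0.1 | 0.1 | 0.1 |
| Third vasopressor added | yes | yes | yes |

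The thresholds agree throughout. For this item the condition is the only difference of substance.

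**2. Illustrative norepinephrine courses within 6 hours (mcg/min).**

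- *On 5 before infusion, raised to 15.* The increase is 15 − 5 = 10, which reaches the threshold. It is an event under all three texts and is always reported.
- *Off vasopressors, started at 10.* The increase is 10 − 0 = 10. On the plain wording it is an event under 6.2.2 and SAP 7.2.2. It is outside the 12.1 list if the condition refers to use before the infusion.
- *Off vasopressors, started at 5, then raised to 15.* From zero the increase is 15; from the first dose it is 15 − 5 = 10. It meets 6.2.2 and SAP 7.2.2 on either count. It meets 12.1 only if the condition refers to the moment of the increase, which 12.1 does not say.
- *Off vasopressors, started at 5 and held.* The increase is below 10 and is not an event under any of the texts.

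The disagreement is therefore confined to patients who go from no vasopressor to at or above a threshold in the window.

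**3. Do the other routes close the gap?** Both remaining general limbs of 12.1 turn on judgement. Section 12.2 can push the same way: Protocol 10.4.1 collects daily, on days 0 through 14, "Vasopressor use (Y/N), lowest systolic blood pressure, creatinine, bilirubin, and platelet count for the day", so a site could treat a new vasopressor need as a systematically captured organ failure and not file it unless it thought the study was responsible.

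**4. Does it reach the analysis and oversight?** SAP 12.7.11 treats pre-specified infusion events as a class of adverse event and lists and counts them. SAP section 8, which sets out derived variables, has no derivation of this event from recorded doses. Sections 5, 9.4, 12.3.3 and 12.5 do not say which definition applies. If the DSMB tally relies on reported events and one of three is not filed, it stands at 3 − 1 = 2 and the trigger is not met.

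**5. Could the event be recovered?** Yes. Protocol 10.3 records vasopressor doses every 15 minutes during the infusion and hourly for the next 5 hours, whether or not an adverse event is filed.

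**The case against.** The strongest reply is that little would be missed. Staff are on site for the 6 hours (Protocol 8.9) and a study physician attends the whole infusion (Appendix H). Section 12.1 counts an event as study related when the timing is reasonable and the procedure could readily have caused it, and new shock soon after the infusion is a strong candidate. The carve-out in 12.2 lifts once an event is considered study related. SAP 12.7.11 says that anticipated as well as unanticipated adverse events will be collected. Finally, an increase in dose can be read as presupposing an existing dose, in which case the three texts largely coincide.

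Much of this stands, and it limits the point. A reader might infer that new shock in a patient off vasopressors cannot be reported, or that the safety endpoint is necessarily undercounted. The documents support neither: the judgement-based limbs remain, the endpoint definitions carry no condition, and the doses are on record. Nor do the documents rank hypotension above the other theoretical harms. Section 12.1 also omits rash from its transfusion-reaction examples, but the criterion is unchanged and nothing turns on that.

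What survives is that a case can meet the endpoint wording and still depend on judgement to be reported, and that the plan does not say how the endpoint count will be assembled. That the wording admits several readings is itself a reason to settle it.

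**Conclusion.** The inconsistency is real and should be resolved. For patients off vasopressors, 12.1 withdraws automatic reporting of an event that 6.2.2 and SAP 7.2.2 count on their plain wording. The adverse-event listing, the safety-endpoint count and the three-subject trigger can then disagree.

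This rests on two readings: that being on a vasopressor means before the infusion, and that a start from zero is an increase. Neither is stated; both are natural.

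The size cannot be estimated, because the documents give no rate of baseline vasopressor use or of new starts. If, purely as an assumption, 40% to 60% of patients were off vasopressors, then 0.4 × 120 = 48 to 0.6 × 120 = 72 patients would fall outside the automatic rule. It would be wrong to read that as 48 to 72 missed events. Only those started at or above a threshold within 6 hours, and judged neither unexpected nor product-associated, would go unreported. With blinding intact there is no reason to expect that judgement to differ by arm. The practical exposure is a lower tally against a trigger of three.

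**What to change.** - Reconcile Protocol 6.2.2, Protocol 12.1 and SAP 7.2.2 to a single definition. State whether a start from zero counts as an increase, and from which reference dose an increase is measured. Because the same event stops the infusion, the sponsor chooses the clinical rule; this review does not propose one.
- Have Protocol 9.4 (infusion stop), 12.3.3 (DSMB notification) and 12.5 (three-subject evaluation, repeated in section 5) cite that definition.
- In the SAP, count the endpoint from the recorded vasopressor doses as well as from reported events, and reconcile the two.

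The cost is a wording change with cross-references, a small derivation from data already collected, and possibly a few more reports.
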